6.0 ADVERSE EVENTS

6.1 Potential risks

6.1.1 The risk of falling: This could be caused by loss of control of the training activity by the participant or therapist as well as malfunction of the SMA device itself. The risk of falling will be minimized by having RIC licensed PT personnel conduct the participant training sessions with manual assistance, gait belt, assistive devices such as cane or a walker as needed. This risk is similar to that during any clinical outpatient physical therapy session.

6.1.2 Discomfort, skin pressure/friction, bruising, pain, or unusual swelling caused by the exoskeleton which has the potential to lead to skin breakdown or abrasions. This risk will be minimized by a thorough skin check performed by RIC's experienced licensed physical therapy personnel at each session. Adjustments to the sizing and placement of

additional padding will be assessed to decrease the risk of skin breakdown as well.

6.1.3 The device itself could malfunction. The device delivers 6-8 Nm (Newton-meter) of torque, which give a gentle assist to movement. In the event of device malfunction, this force will be absent and the subject will be given with physical assistance if required, and the patient will be able to safely transfer out of the device, if required. Research engineers will ensure that the device has been maintained according to specifications and the software is always in working order.

6.1.4 Muscle soreness from exercises during therapy sessions. All subjects will work with RIC's licensed physical therapy personnel and will be initiated with testing and therapy sessions with simple activities, progressing on to more dynamic, complex activities when it is clear that they are safe and acclimated to the protocol being used. To manage this, subject will be provided with adequate rest periods and subjects will be monitored by questions regarding discomfort.

6.1.5 Risks associated with TMS:

There are certain populations who have a risk of seizures following TMS. Individuals will be screened using the TMS safety checklist. Single pulse TMS has been deemed to "carry little risk beyond occasionally causing local discomfort" in healthy adult populations (Anand and Hotson 2002). Our stimulation procedures follow published safety guidelines. Seizure activation is extremely unlikely with the single pulse low numbers of stimulation proposed in the current investigation.

A small number of people find TMS uncomfortable, particularly at high intensities of stimulation. If subjects report feelings of discomfort stimulation intensity will be reduced or, if not feasible, testing will be terminated. The "clicking" noise associated with stimulation may also be uncomfortable for some individuals. All subjects will be provided with protective ear-plugs during stimulation.

There is a possibility that a subject could develop muscle soreness or fatigue from holding a tonic contraction. If shoulder, wrist or leg pain occurs as a result of the experiment, we will withdraw the subject from the study. During testing, there is also a possibility that a subject may experience irritation due to the nerve stimulation or EMG electrodes or electrode gel.

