
Change surface/stance:
 
 • Level surfaces • Over obstacles • Over compliant surfaces • Tandem walk (forwards/backwards) • With/without AFO Multidirectional walking: • Backwards • Tandem Dual tasking with gait: • Ball catch • Ball bounce • Cognitive tasks Other Gait challenges: • Increased speed, stopping and starting • Pivot turns • Balance beam • Perturbations • Obstacles • Increased distance • Assistive device progression • Reduction in physical assist progression Functional up right postures • Stairs • Ramps, curbs • Outdoors/community 	
 • Intensity: RPE minimum 12 up to 16 on 6-20 RPE scale • Or HR up to 75% of Age predicted max (220-age) • PT will consider Beta blockers and Ca channel blockers for HR 	
 • Will be customized based on same parameters for both groups: on high intensity gait training • Intensity 12-16 RPE or HR 70% APMHR • Frequency & Duration– initially determined by PT according to pt's functional ability • To work towards 45 min/once a day/at 12-15RPE at d/c

Response Criteria / Outcome Measures:

The following outcome measures will be evaluated for both the groups at testing points at baseline, mid-testing, post-testing and follow-up testing.

Clinical Performance Outcome Measures:

1. **6 Minute Walk Test:** The 6MWT measures the distance a subject can walk indoors on a flat, hard surface in a period of 6 minutes, using assistive devices, as necessary. The test is a reliable and valid evaluation of functional exercise capacity and is used as a sub-maximal test of aerobic capacity and endurance. The minimal detectable change distance for people with sub-acute stroke is 60.98 meters.¹⁴

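### The plan lists risks but does not ask about falls and adverse events in the same way in both arms, and plans no by-arm summary of them

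*Combined protocol and SAP*

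**What the plan says.** **Risks.** Section 6.0 has one subsection, 6.1 Potential risks. On falls, 6.1.1 gives two kinds of cause: losing control of the exercise, "as well as malfunction of the SMA device itself". Its mitigation is that "The risk of falling will be minimized by having RIC licensed PT personnel conduct the participant training sessions with manual assistance, gait belt", plus walking aids as needed. It then sets a benchmark: "This risk is similar to that during any clinical outpatient physical therapy session".

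**Checks that exist.** 6.1.2 has a skin check at each session, for harm from the exoskeleton. 6.1.4 has questions about discomfort. 6.1.5 has rules for discomfort and pain during TMS. 5.2 includes a 0-10 pain score and says sessions are documented in Cerner. 4.4 records why and when a participant was removed.

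**Removal.** 5.4.5 removes a participant when an adverse event makes it unsafe to go on.

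**Analysis.** 8.3 compares the outcomes listed in 5.2 within participants and between groups by ANOVA. It does not mention falls or adverse events.

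**Home programme.** 5.2 gives a home exercise programme to both arms: "Will be customized based on same parameters for both groups: on high intensity gait training". Its intensity is "Intensity 12-16 RPE or HR 70% APMHR". Frequency and duration are "initially determined by PT according to pt's functional ability", with the aim "To work towards 45 min/once a day/at 12-15RPE at d/c". The training intensity for both groups' sessions is "RPE minimum 12 up to 16 on 6-20 RPE scale", or a heart rate up to 75% of the age-predicted maximum.

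**Entry.** 3.1 requires a gait speed above 0.4 and below 0.8 m/s, and admits people who need one person's help to walk 10 m. It also requires physician approval and the ability to do the home programme where they live.

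**The concern.** The protocol names a device-related cause of falls and has a removal rule triggered by adverse events. It states no common step by which either would become known. Treating therapists see participants three times a week and may hear of some events. But what they hear depends on what they happen to ask, and one of the few fixed per-session checks looks for exoskeleton harm. Recorded events could therefore be fewer than those that occurred, and could be noticed unequally in the two arms.

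The trial could then report a change in walking speed with no fall or injury table beside it. Events that were not asked about uniformly cannot be reliably reconstructed at analysis.

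The home programme is a secondary matter. The protections in 6.1.1 depend on a therapist being present, and the home sessions are not described as having one.

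**Working it through.** The plan gives no fall rate, adverse-event rate or safety sample size, so there is no stated figure to reproduce. The check is a count and a side-by-side reading.

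1. **Schedule (5.3).** The rows are inclusion/exclusion, consent, history and examination, training protocol, clinical performance measures, self-reported measures, and TMS. That is 7 rows, of which 0 cover falls or adverse events.

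2. **Outcomes (5.2).** 7 clinical performance + 7 self-reported + TMS = 15 named outcomes (item 16 is blank). The Berg Balance Scale, mFES and ABC concern balance, fall risk or confidence, and item 12 is pain. Outcomes that count falls or adverse events: 0 of 15.

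3. **Analysis (8.3).** Its scope is the 5.2 list, so by step 2 it produces no fall or adverse-event comparison. The pain score is compared by arm.

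4. **Do the existing checks fill the gap?**
   - Skin check: every session, but directed at exoskeleton harm, so it bears mainly on the SMA arm.
   - Discomfort questions: no form, schedule or fall item is given.
   - Cerner notes: no fall or adverse-event item is specified.
   - Removal record (4.4): captures only events that end participation.
   - TMS rules: apply only to the TMS sessions.

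   None asks about falls in the same way in both arms. After session 18 the thrice-weekly contact ends, and no route is stated for events before the 3-month visit.

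5. **Home against clinic.** Fall precautions in 6.1.1: therapist, manual help, gait belt and aids in clinic; none stated for home. RPE: 12-16 in clinic; 12-16 at home, and 12-15 at discharge. Heart rate: up to 75% of the age-predicted maximum in clinic; 70% at home. Home intensity is thus set equal or somewhat lower, with no fall precaution of its own.

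6. **What a by-arm table could show.** With 0 events in n participants, the one-sided 95% upper bound on the risk is 1 - 0.05^(1/n).
   - n = 40: 1 - 0.05^(1/40) = 7.2%.
   - n = 28 (40 x 0.70, taking 5.1's 30% attrition as equal in both arms): 1 - 0.05^(1/28) = 10.1%.

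   The table would describe the events; it could not establish equal safety.

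**The case against.** The strongest reply is that participants are not left unprotected. They walk at 0.4 to 0.8 m/s, which 1.1 classes as limited community ambulation. They live in the community, travel to clinic, have physician approval, and must be able to do the home programme. The therapist sets the starting home dose, and the home heart-rate figure is lower than in clinic. Institutional event reporting may also operate outside the protocol, and home instructions may stand in consent pages that are not in the text reviewed.

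Most of this stands against the home point, which is therefore secondary. It does not answer the ascertainment point. The documents neither describe nor cite an outside reporting system, and such a system would not by itself give comparable counts by arm.

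A reader might be tempted to go further in three ways, none of which the documents support:
- *That home training outweighs clinic training, so most exposure is unprotected.* The 45 minutes a day is a goal to work towards by discharge, and the therapist sets frequency and duration at the start. No minutes-per-week comparison can be drawn from that, and none is needed.
- *That the device raises fall risk at home.* The synopsis and 7.1 describe it for therapy sessions. The home gap applies to both arms; the device question belongs to the sessions.
- *That no safety information is collected.* Some is, as set out above. It is partial and not uniform.

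**Conclusion.** The point holds as a gap in ascertainment and reporting: 0 of 7 schedule rows, 0 of 15 named outcomes, and no by-arm summary in 8.3. This conclusion is firm, because it rests on sections that run continuously from 6.1.5 to 7.0 with no sign of removed text.

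The home-precaution point holds more narrowly, as a statement about what 6.1.1 covers. It assumes that no home fall instructions are given elsewhere, which cannot be confirmed without the consent pages.

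A reader might infer that the primary comparison is compromised. It is not: nothing here alters the gait-speed measurement, its analysis or the sample size. Nor do the documents show that either arm is less safe. This is a cheap improvement that should be made before enrolment, because the information cannot be reliably recovered later.

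**What to change.** - **5.3:** add a fall/adverse-event row. At every therapy session the treating therapist asks the same short scripted question in both arms: any fall (in session or at home), injury, skin problem or medical visit. At mid, post and 3-month testing, and at each TMS visit held, the participant completes a form, so that the blinded assessor does not ask.
- **Align the schedule:** 5.3 marks TMS at follow-up, but 3.1 and the 5.2 flow table give two TMS sessions. 4.3 rules out follow-up after session 18, whereas 2.3, 5.2, 5.3 and 8.3 include a 3-month visit.
- **Section 6.0:** report injurious events promptly to the Principal Investigator.
- **8.3:** tabulate falls and adverse events descriptively by arm and setting, without a significance test.
- **6.1.1:** add a home precaution for participants who need walking assistance, such as practising only with a helper, or supported exercise until the therapist clears them. The choice is clinical.

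**Cost.** Contacts per participant: 18 sessions + 3 test visits + 2 or 3 TMS visits = 23 or 24. At an assumed one minute each for 80 participants: 80 x 23 = 1,840 min, or 30.7 hours; 80 x 24 = 1,920 min, or 32 hours. Data entry, form handling and event reporting come on top. No visits are added.

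**Limits that remain.** The session questions are asked by staff who know the arm. Events after session 18 depend on recall at the 3-month visit. Without a log of home practice there is no exposure denominator for home falls. At 40 per arm the comparison stays descriptive.

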7.0 DEVICE INFORMATION

7.1 Device

- Other names for the device: Walking Assist Device with Stride Management System
- Classification - type of device: Walking Assist Device
- Mode of action: This device is a light weight design with 2 DC motors can generate torque up to 6 Nm, worn around hips and thighs to provide assistance during walking.

- Storage and stability: Weighs 2.8 kgs and easy to store in a cabinet
- Protocol dose: 45-60 min sessions ,3x/week for 6-8 weeks
- Preparation: Belt like device to be worn around hips and thighs
- Availability: Provided by Sponsor (free of Charge)

8.0 STATISTICAL CONSIDERATIONS

8.1 Study Design/Study Endpoints

This proposed study is a randomized control trial to compare Task Specific Training with SMA and Impairment based Physical Therapy on Functional Walking Ability in Outpatient Stroke Rehabilitation setting.

8.2 Sample Size and Accrual

A total enrollment of 80 subjects is estimated for this study. Each enrolled subject is randomly assigned to either one of the groups (SMA or IPT; 40 participants per group). A detailed description of study procedures and study endpoints are provided in section of 5.0

8.3 Data Analyses Plans

The outcome measures for each subject (listed in Section 5.2) are recorded during 0th, 10th and 18th session of the training cycle and at 3 month follow up visit. Photographs and video without individual subject's faces will be recorded as this device is not commercially available yet and dissemination of accurate information will be assisted by showing how the device operates when donned and used by subjects. Outcome measures are compared with in the subject and across the subject pools for statistical significant differences using Multiple ANOVAs. All the statistics will be performed at 90% confidence level.

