Title	Randomized Control Trial Comparing Walking Task Specific Training with Stride Management Assist (SMA) Device vs. Functional Task Specific training on Functional Walking Ability in Outpatient Stroke Rehabilitation.
Short Title	Impairment vs. Functional Walking Training in Sub-Acute and Chronic Stroke (match this to title used it ClinicalTrials.gov)
Protocol Number	STU00085161
Methodology	Randomized Controlled Trial with 2 arms
Study Duration	1 year
Study Center(s)	Single site, multiple clinics within RIC's flagship hospital and it's outpatient clinics
Objectives	Determine if Honda Stride Management Assist vs. traditional Functional Gait Therapy increases Gait speed and function post stroke
Number of Subjects	80
Diagnosis and Main Inclusion Criteria	Cerebrovascular accident (CVA), post 30 days, Gait speed between 0.4 m/s and 0.8 m/s, MMSE > 17, unsupported sitting >30 s, walk at least 10m with up to max assist, follow instructions, physician clearance for participation
Study Product(s), Dose, Route, Regimen	Honda Stride Management Assist device in outpatient physical therapy
Duration of administration	18 Sessions of Outpatient Physical Therapy + 4 Sessions of testing
Reference therapy	Traditional Functional Mobility Training Physical Therapy
Statistical Methodology	Multiple ANOVAs

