2.0 STUDY OBJECTIVES

2.1 Primary Objectives

- 2.1.1 To determine the effect on gait speed, as assessed by the 10 meter walk test of the SMA device vs. traditional physical therapy care in an outpatient setting for post stroke individuals.

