3.1 Inclusion Criteria

- \geq 30-days post stroke
- Age: 18-85 Years
- Initial gait speed of > 0.4 m/s and < 0.8 m/s
- Adequate cognitive function (MMSE score > 17)
- Subject is willing to be randomized to the control group or the treatment group.
- Ability to sit unsupported for 30 seconds
- Ability to walk at least 10m with maximum 1 person assist,
- Ability to follow a three-step command
- Physician approval for patient participation
- Living in the community post-stroke with ability to travel to the intervention site to participate in the outpatient program and able to perform the HEP program in the residential facility.
- Willing to carry wireless body sensors through the period of the study and to follow-up time period, post inpatient stroke, cardiac, pulmonary, or any other lower extremity physical rehabilitation

- \geq 90 days post major orthopedic surgery (i.e. hip, knee, and/or ankle joint replacement)
- \geq 6 months post CABG or cardiac valve procedure
- Able and willing to give written consent and comply with study procedures, including follow-up visits
- Willing to participate in two Transcranial Magnetic Stimulation sessions if they meet compatibility requirement.
- Cannot not be participating in any other structured outpatient or home health physical therapy program

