5.0 STUDY PROCEDURES

5.1 Screening/Baseline Procedures

Subjects will be randomized into 2 separate groups, either SMA or IPT. We will enroll 80 subjects, 40 in each group, planning for a 30% attrition rate. These subjects will be recruited when they are referred to RIC's stroke rehabilitation outpatient clinics at RIC's flagship at [name], or RIC Northshore in Northbrook IL or RIC Willowbrook in Willowbrook, IL. We will also recruit from local physicians or RIC's Clinical Neuroscience Research Registry for subjects who are potential candidates for outpatient physical therapy. They will be directed to a physical therapist who will inform them of the time commitment required and questioned regarding the inclusion/exclusion criteria. Once subjects have agreed to participate in the study, they will come to RIC and be consented at one of the clinics at the Rehabilitation Institute of Chicago. Study staff will explain the study, a written consent form will be signed by the subject and witnessed by study researchers, a copy will be given to the subject and a copy will be kept in the subject's folder in a secure, locked cabinet in the lab's locked office.

After consenting, subjects will undergo a physical evaluation and screening exam by a licensed PT. If they meet study criteria, they will be randomly placed into either the SMA group or the IPT group using a random number generator and they will be entered into the study. Once they are enrolled, baseline outcome measures will be assessed by a blinded research PT.

In addition, subjects will have a baseline measure of their cortical excitability through TMS. This will be conducted at University of Illinois, Department of Physical Therapy. TMS sessions will last approximately 2 hours.

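### The plan names ANOVA as a method but not the primary visit, the between-arm contrast, the walking pace or the handling of missing outcomes, so the primary result is not fixed in advance

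*Combined protocol and SAP*

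**What the plan says.** The synopsis row for statistical methodology reads "Multiple ANOVAs" and nothing more. Section 8.3 expands this to "Outcome measures are compared with in the subject and across the subject pools for statistical significant differences using Multiple ANOVAs" and adds "All the statistics will be performed at 90% confidence level". It lists outcomes as "recorded during 0th, 10th and 18th session of the training cycle and at 3 month follow up visit".

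The primary objective (section 2.1) is "To determine the effect on gait speed, as assessed by the 10 meter walk test of the SMA device vs. traditional physical therapy care". It names the instrument and the arms, but no visit and no pace. Section 2.3 calls all four assessments endpoints. The 10 meter walk entry in section 5.2 has the test done at both self-selected and maximum safe pace and asks only that the pace be documented. Section 1.1 bases its ambulation classes on self-selected speed, and section 3.1 uses the same limits for entry ("Initial gait speed of > 0.4 m/s and < 0.8 m/s"). Self-selected pace is therefore implied, but it is nowhere declared primary.

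Attrition appears once, in section 5.1: "We will enroll 80 subjects, 40 in each group, planning for a 30% attrition rate". No section gives an analysis population or a missing-data method. Section 5.4 lists reasons for removal that include adverse events and non-compliance. Section 5.1 places the baseline outcome test after randomisation: "Once they are enrolled, baseline outcome measures will be assessed by a blinded research PT".

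**The concern.** ANOVA is a family of tests. The sentence in section 8.3 could mean separate across-group ANOVAs at each visit, a repeated-measures ANOVA with a group-by-time term, or an ANOVA on change scores. Each can be run at either pace, and most at more than one visit. These readings answer different questions and can give different answers on the same data, so the primary result could be chosen after the data are seen.

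Three further matters follow from the gap.

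- An across-group ANOVA at one visit leaves out the baseline speed that the trial already collects.
- A repeated-measures ANOVA in its standard form drops anyone who misses a visit, including people who were tested at the visit of interest.
- Baseline is tested after allocation, so some randomised participants may have no baseline test, and the plan does not say what happens to them.

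**Working it through.** **The stated figure.** The enrolment of 80 cannot be reproduced, because section 8.2 gives no effect size, SD or power. Only the attrition arithmetic can be checked: 80 × 0.70 = 56, or 28 per arm, and 56 / 0.70 = 80. The document does not state 56. I use 28 per arm as the planned number remaining.

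**Inputs from the document.** The 90% level is taken as two-sided alpha 0.10. There are three post-baseline visits and two paces. The 10 meter walk entry gives 0.06 m/s as a small and 0.14 m/s as a substantial meaningful change. The entry window is 0.4 to 0.8 m/s.

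**Assumed, because the document gives none.** SDs, correlations between visits and between paces, the shape of the effect over time, and the timing of attrition.

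**Chance of at least one false positive if any contrast could count.**

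- Independent tests: 1 − 0.9³ = 0.271 for three visits; 1 − 0.9⁶ = 0.469 for three visits by two paces.
- Three visits at one pace, simulated as baseline-adjusted contrasts with visit correlation 0.5-0.7: about 0.24-0.27.
- Six contrasts, same visit correlations, between-pace correlation 0.7-0.9: about 0.33-0.39.
- Six unadjusted contrasts, visit correlation 0.5-0.8: about 0.25-0.36.
- One pre-specified contrast: 0.10.

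**Across-group ANOVA at Post Testing against ANCOVA, 28 per arm.** The standard error of the difference is SD × √(2/28) = 0.267 × SD. ANCOVA replaces SD by SD × √(1 − ρ²), where ρ is the correlation of baseline with Post.

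- Effect 0.6 SD, ANOVA: 0.6 / 0.267 = 2.25, power about 0.72-0.73.
- Effect 0.6 SD, ANCOVA: the SD factor is 0.866, 0.800 or 0.714 for ρ = 0.5, 0.6 or 0.7. Simulated power is 0.81, 0.87 or 0.93.
- Effect 0.14 m/s, assumed Post SD 0.20, ANOVA: 0.14 / (0.267 × 0.20) = 2.62, power about 0.83.
- Same case, ANCOVA: a uniform baseline over the entry window has SD 0.4/√12 = 0.115. If the gain is independent of baseline, ρ = 0.115/0.20 = 0.58 and the residual SD is 0.20 × √(1 − 0.333) = 0.163. Power is about 0.94 by formula and 0.93 by simulation.

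**ANCOVA against a group-by-time test.** With 28 per arm, the direction depends on the scenario.

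| Scenario | ANCOVA at Post | Group-by-time |
|---|---|---|
| 0.6 SD at Post, held to 3 months | 0.81-0.93 | 0.70-0.89 |
| 0.6 SD at Post, falling to 0.3 SD | 0.81-0.92 | 0.57-0.78 |
| 0.6 SD at Post, rising to 0.9 SD | 0.81-0.93 | 0.91-0.99 |
| Entry window, 0.14 m/s held, Post SD 0.20 | 0.93 | 0.96 |

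**People kept in the analysis.** If more than 28 per arm are observed at Post, ANCOVA can use them all. In the 0.6 SD case, power is 0.86-0.95 with 32 per arm and 0.92-0.98 with 40.

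**Missing values.** Suppose a fraction of one arm is missing and would have walked slower than predicted by a fixed amount. The arm difference then moves by the product: 0.20 × 0.06 = 0.012 m/s, up to 0.30 × 0.14 = 0.042 m/s. Divided by 0.06, that is 20% to 70% of the small meaningful change.

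**The case against.** The best reply is that ANOVA is a valid method, that the primary outcome is named, and that attrition was allowed for. All three are true, but none settles which test decides the trial. The attrition allowance affects the enrolment count only.

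The other side is right on several points, and they limit what can be said.

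- **The intended model.** A reader might infer that a four-visit repeated-measures ANOVA is planned and that it will discard 24 of the 80. The wording fits separate ANOVAs per outcome or visit equally well, and those need not drop anyone for missing another visit. The 30% is a planning rate, so the number lost to a complete-case analysis could be higher or lower.
- **Group-by-time as an error.** If the arms are equal at Post but 0.6 SD apart at 3 months, group-by-time is significant in 73-91% of simulated trials and ANCOVA at Post in about 10%. It is tempting to call the former false positives. They reflect a real 3-month difference, and no section makes Post Testing primary.
- **ANCOVA as always stronger.** The table shows it is not. The gain holds against an unadjusted ANOVA at Post only.
- **The error rates as the trial's own.** They apply only if success may be claimed on any contrast, which no section says. Part of the rate also comes from the 90% level, which is a separate issue.
- **The pace.** Sections 1.1 and 3.1 point to self-selected speed, so this gap is the smallest of the four.
- **Missing-data bias.** The 20-70% shift is a one-arm worst case; equal departures in both arms cancel. Section 5.4 ties the end of follow-up to withdrawn consent only, so removal need not mean a missing outcome.

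**Conclusion.** The point stands as an omission that should be closed before analysis. The primary visit, the between-arm contrast and the missing-data handling are absent from the whole document, and the pace is implied but not declared. That conclusion rests on the text and needs no assumed figure.

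Its size does rest on assumptions. The false-positive chance is about 24-27% (one pace) or 25-39% (two paces) against a nominal 10%, if any contrast could be claimed. Adjusting for baseline raises power at Post from about 0.72 to 0.81-0.93 in the 0.6 SD case, and from about 0.83 to 0.94 for 0.14 m/s at an assumed SD of 0.20. Against a repeated-measures reading, the benefit is a contrast fixed in advance that uses everyone observed at the named visit, and no power gain is claimed. The choice of Post Testing as the primary visit is a proposal; the sponsor has not stated one.

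**What to change.** 1. In the synopsis and section 8.3, define the primary analysis as the SMA-minus-IPT difference in self-selected 10 meter walk speed at one named visit, adjusted for baseline speed by ANCOVA, on all participants observed at that visit and analysed as randomised. Post Testing is proposed because it marks the end of the 18 sessions and appears in every version of the schedule, whereas section 4.3 denies the 3-month visit.
2. Label the other visits, the other pace and within-arm changes as secondary or descriptive.
3. State the missing-at-random assumption, and add one sensitivity analysis that shifts missing values in one arm by 0.06 and 0.14 m/s. Report attrition by arm and visit.
4. In section 5.1, place the blinded baseline test before randomisation. The eligibility gait speed is only a fallback: the screening examiner is not stated to be blinded and section 3.1 names no pace.
5. Reconcile the schedule: section 4.3 with sections 2.3, 5.2 and 8.3 on the 3-month visit; the outcome list in section 5.2 (all measures at four points) with the table in section 5.3 (no mid-test for self-reported measures or TMS); and the tenth session in section 8.3 with the test after Session 9 in section 5.2.

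Cost: small protocol and SAP edits, a reordering of steps already planned, and one extra analysis. No new visits are needed. The other visits lose any claim to primary status.
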